9.4.1. Primary Endpoints Analyses

Safety analyses will be performed on data from all participants in the Safety Population.

The incidence of AEs and SAE will be tabulated by dose and overall across dose groups. The rate of occurrence for each adverse event will be summarized by body system, severity, and relation to the administration of PF-07055480. All serious adverse events will be summarized separately.

Additional descriptive analyses to support the primary endpoint will include changes from baseline in clinical laboratory variables (including FIX inhibitor and laboratory parameters for thrombotic potential), vital signs, and vector shedding analysis.

The time course profile of FVIII activity will be determined by measuring changes in circulating FVIII activity.

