9.4.3. Exploratory Endpoints Analyses

The impact of potentially relevant circulating factors on FVIII activity will be assessed by summarization of vWF, CRP, IL6, and FVIII antigen. Immune response will be studied by measuring neutralizing activity and antibodies to AAV2/6, as well as Interferon-gamma ELISPOT.

Change from the preceding year values may be calculated for selected clinical and laboratory parameters. Shift-tables (change-from-baseline relative to the normal range) may be constructed for selected laboratory parameters. Participants will continue to be followed for years 2 through 5 to gain additional data on safety and durability of effect.

Details for additional exploratory endpoint analyses (eg. optional liver biopsy) will be provided in the SAP.

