### 3.1.2.1. Factor VIII Activity Geometric Mean

The primary endpoint of time course profile of FVIII activity will be determined for the participants in the cohort administered the dose level intended for Phase 3 (ie, Cohort 4,  $3 \times 10^{13}$  vg/kg). The geometric mean for each participant will be calculated and summarized with descriptive statistics across the cohort for each assay type, for each year of the study. The geometric mean is the antilog of the mean of the log-transformed values.

FVIII activity over time will be calculated for each participant as the geometric mean of all eligible FVIII activity measurements within each yearly window. The summary statistics across participants in each cohort, for each observation period, will include sample size, arithmetic mean, standard deviation, median, first quartile, third quartile, minimum, and maximum. Calculation of the geometric mean for Year 1 will use all available data points beginning with the week considered to be when ‘steady state’ (see [Section 3.3.5](#) for more detail) has been achieved (eg, Week 9), through Week 52 (Weeks up to 53 will be included per the Schedule of Activities [SoA]), including those measured at unscheduled visits, and those where multiple observations may fall into the same time window. If multiple eligible FVIII activity observations are collected on the same day, the average level of these observations will be used for the given day. FVIII activity measurements within 96 hours after a FVIII replacement infusion, as well as those collected after routine prophylaxis has been initiated or resumed, will be excluded.

The geometric mean of FVIII activity will be similarly calculated for each assay type in the following designated yearly time periods (allowing for the 1 month flexibility in the SoA visit schedule after the first year) as indicated below:

Time period	Geometric Mean Window
Week 54 through Week 108 (Week $104 \pm 4$ weeks)	FVIII Activity Year 2
Week 109 through Week 160 (Week $156 \pm 4$ weeks)	FVIII Activity Year 3
Week 161 through Week 212 (Week $208 \pm 4$ weeks)	FVIII Activity Year 4
Week 213 through End of Study (Week $260 \pm 4$ weeks)	FVIII Activity Year 5

If a participant has not yet been followed for the full interval or has missing data, then all available data will be included to calculate geometric mean despite the missed measurements.

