### 3.3.5. FVIII Steady State

Due to the small sample size and high inter-subject variability of PF-07055480 transgene expression, including FVIII activity levels, both mean and median values of FVIII levels using chromogenic and one-stage assays will be presented for each visit to assist in determining the onset of steady state of transgene expression.

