### **6.1.2. FVIII Activity**

Summary tables for central laboratory FVIII activity values, with descriptive statistics by study visit and dose level will be created. The FVIII activity values assessed by the two assays (chromogenic and one-stage clotting) will be summarized separately. Listings will be presented separately for local and central laboratory individual values, as described in [Section 3.1.2](#).

Individual plots of FVIII activity will be created using the Safety population, with collection time in weeks post-infusion on the x-axis (including unscheduled visits), and FVIII activity on the y-axis. Separate figures will be created for one-stage clotting and chromogenic results; each figure will contain all participants from a cohort on the same graph. The plots will be created using both the original scale and the log scale.

A scatter plot of chromogenic assay versus one-stage assay results will be generated to investigate the correlation between the two assays. Measurements from all time points will be placed on the same graph, and thus a participant will contribute multiple times to the figure. Data points will be differentiated by different colors for cohorts and symbols for participants.

All FVIII analyses will be performed using the Safety analysis set. Additional analyses may be performed using an Evaluable population, if appropriate.

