#### **6.1.2.1. FVIII Activity Geometric Mean**

The geometric mean of FVIII activity between the week determined to be the start of steady state (Week 9), and Week 52 (Year 1) will be summarized for Cohort 4 ( $3 \times 10^{13}$  vg/kg) by type of assay (chromogenic and one-stage). The geometric mean of FVIII activity will also be summarized for each additional yearly interval as specified in [Section 3.1.2.1](#).

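### Durability of FVIII activity has no committed within-participant measure: the yearly Cohort 4 tables are marginal summaries, imprecise for decline and able to understate it

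*Protocol*

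**What the plan says.** Protocol 9.4.1 words the FVIII primary endpoint as change: "The time course profile of FVIII activity will be determined by measuring changes in circulating FVIII activity". Protocol 9.4.3 gives the reason for the long follow-up: "Participants will continue to be followed for years 2 through 5 to gain additional data on safety and durability of effect". The same section allows, without requiring it, a year-on-year comparison: "Change from the preceding year values may be calculated for selected clinical and laboratory parameters". FVIII activity is not named there.

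The SAP plans the following for FVIII activity:

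- By visit (6.1.2): "Summary tables for central laboratory FVIII activity values, with descriptive statistics by study visit and dose level will be created". These are values, not changes. SAP 3.1.2 defines a baseline, but no FVIII summary uses it to form a change.
- By year, for Cohort 4 (3.1.2.1): "FVIII activity over time will be calculated for each participant as the geometric mean of all eligible FVIII activity measurements within each yearly window". Each year is then described across participants by sample size, arithmetic mean, SD, median, quartiles and range. SAP 6.1.2.1 confirms this: "The geometric mean of FVIII activity will also be summarized for each additional yearly interval as specified in" Section 3.1.2.1.
- Individual displays: plots over time for the Safety population on original and log scales (6.1.2), a listing of every value (3.1.2), and Cohort 4 profiles with liver tests and steroid use (6.5.4).

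SAP 3.1.2 and 3.1.2.1 drop FVIII values from the summaries, geometric means and plots once a participant starts or returns to prophylaxis. The listing keeps them, flagged.

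**The concern.** The question that Years 2 to 5 are meant to answer is how much of a participant's own FVIII activity remains. The SAP derives the two quantities needed (that participant's geometric mean in each year) and stops before comparing them.

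This is out of line with the rest of the SAP. It specifies a within-participant difference or a change from baseline for annualized infusion rate (3.2.1), total annualized bleeding rate (3.2.2), EQ-5D-5L (6.2.3), von Willebrand factor (6.3.3) and liver tests (6.6.2). An exploratory marker gets a change summary; the primary FVIII measure does not.

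Two things are at stake. First, SAP 3.3.5 refers to "high inter-subject variability of PF-07055480 transgene expression". That remark is made about judging when steady state begins, but the same spread sits in every yearly mean and SD, and it cancels only when each participant is compared with himself. Second, the exclusion after prophylaxis means that different participants may contribute to different years. If those who lose expression are the ones who leave the table, the yearly means fall more slowly than individual participants do.

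With no stated measure, the reference for any durability claim (Year 1, preceding year or peak) also stays open in an open-label study in which the sponsor may review data as it accrues (Protocol 9.5).

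**Working it through.** The documents state no SD, between-year correlation, expected decline or Cohort 4 size, so there is no planned figure to reproduce. What follows is illustration under stated assumptions.

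**1. An assumed spread.** Protocol 4.3 associates the starting dose with 12% activity in a non-human primate study and predicts more than 5% activity in 57% of participants. If activity were log-normal with mean 12% (an assumption), then ln 12 − s²/2 = ln 5 + 0.176s, where 0.176 = z(0.57). Since ln(12/5) = 0.8755, s = −0.176 + √(0.176² + 2 × 0.8755) = 1.16. Both figures concern 9×10¹¹ vg/kg; Cohort 4 received 3×10¹³ vg/kg (SAP 6.5.3), about 33 times higher. So 1.16 is a convenient value, not an estimate for Cohort 4.

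**2. Precision of a Year k / Year 1 ratio, n = 5 (assumed).** The 95% factor is the exponential of the half-width on the log scale.

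- Years read as separate samples: t(8) × s × √(2/n) = 2.306 × 1.16 × 0.632 = 1.69, factor **5.4**. With s = 0.7 the factor is 2.8.
- Paired within participant: t(4) × s × √(2(1 − ρ)/n), with t(4) = 2.776:
  - ρ = 0.5: 2.776 × 0.519 = 1.44, factor **4.2**
  - ρ = 0.8: 2.776 × 0.328 = 0.91, factor **2.5**
  - ρ = 0.95: 2.776 × 0.164 = 0.46, factor **1.6**

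**3. Sensitivity to n and s.** At n = 5 and s = 1.0 the factor is 4.30 unpaired, against 3.46, 2.19 and 1.48 paired at the same three correlations. Over n = 4 to 8 and s = 0.6 to 1.4, the unpaired factor runs from 1.90 to 11.27 and the paired factor at ρ = 0.8 from 1.37 to 4.09. Pairing is tighter in every case examined. How much tighter depends on ρ: the standard error shrinks by 1.41, 2.24 and 4.47 times at ρ = 0.5, 0.8 and 0.95.

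**4. Effect of changing contributors.** Take five invented Year 1 values of 150, 80, 40, 15 and 8%, each falling 30% a year. As an arithmetic device only, not a clinical threshold, treat a value below 5% as excluded because of prophylaxis.

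- Year 2: 105, 56, 28, 10.5, 5.6 (n = 5), mean 41.0, median 28.0.
- Year 3: 73.5, 39.2, 19.6, 7.35; the fifth value, 3.9, is excluded (n = 4), mean 34.9, median 29.4.

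The mean falls by 1 − 34.9/41.0 = 15% and the median rises, although every participant fell by 30%. The within-participant ratio in the four remaining pairs is 0.70.

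**The case against.** The strongest reply is that for a handful of participants the individual trajectories are the proper display of durability, and the SAP plans them. On a log axis a vertical drop is the within-participant ratio. This stands: a reader might infer that the plan is blind to decline, and it is not. What the plots do not supply is a prespecified number, and they too stop at prophylaxis.

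A reader might also call the yearly tables cross-sectional. They are not: the values are derived per participant in the same people over time. If everyone contributed to every year, the difference between two yearly arithmetic means would equal the mean within-participant absolute difference. That also stands. But it gives no spread of individual changes and no relative change, it is weighted to the highest expressers, and the equality fails once contributors differ between years. Nor are the tables always insensitive: for a 70% fall with n = 8 and log SD 0.6, an unpaired comparison would have power 0.96.

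Next, SAP 5.1 plans no formal inference, so no interval for a yearly ratio is planned and the factor of 5.4 describes one way of reading the tables. This is correct, and the figures above serve only as illustration.

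Finally, Protocol 9.4.3 is permissive and does not name FVIII, so the SAP breaks no commitment. Agreed: the point is an omission, not a contradiction.

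**Conclusion.** The point holds in a limited form. Neither document commits to a numerical within-participant change in FVIII activity, although change is how the primary endpoint is worded and durability is a stated reason for Years 2 to 5. Trajectories will be visible in plots and listings. The yearly Cohort 4 tables are marginal summaries: imprecise for within-participant decline when spread between participants is high, and able to understate decline when contributors change.

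The size cannot be fixed from the documents. Under the assumptions above (n = 5, log SD 1.16), pairing moves the 95% factor from about 5.4 to between about 4.2 and 1.6 as the between-year correlation goes from 0.5 to 0.95. At the low end the gain is modest. The understatement of decline is shown only in an invented example; its direction and size in the trial depend on who returns to prophylaxis and when.

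The documents do not support the stronger conclusions that decline cannot be shown or that a planned analysis has been dropped. This is a worthwhile, low-cost addition to a descriptive plan.

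**What to change.** In SAP 3.1.2.1 and 6.1.2.1, for each Cohort 4 participant and each assay, derive the ratio of each later year's geometric mean to (a) the Year 1 geometric mean and (b) the preceding year's, among participants with both values. Summarise descriptively as geometric mean ratio, median and range, with the number of pairs and the number excluded because of prophylaxis. List the individual ratios. State that the ratios describe only participants still contributing eligible values, so that they are not read as durability for the whole cohort.

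The cost is SAP wording, two derived ratios, one table and one listing. All inputs are already derived. No new data collection or hypothesis test is needed, and Protocol 9.4.3 already leaves room for the year-on-year comparison.

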9.5. Interim Analyses

An interim analysis of safety and efficacy data will be conducted at 1 year after the last enrolled participant receives SB-525 (PF-07055480) infusion. As this is an open-label study, the sponsor may conduct unblinded reviews of the data during the course of the study for the purpose of safety assessment, facilitating dose-escalation decisions, facilitating pharmacokinetic (PK)/pharmacodynamic (PD) modeling, and/or to support clinical development.

9.6. Data Monitoring Committee

This study will use an external data monitoring committee (DMC). The DMC is independent of the study team and includes only external members. The DMC will convene approximately every 6 months until study completion to monitor the safety and efficacy of the participants. Ad-hoc meetings will be organized as needed (eg, to assess events of special interest or after receipt of a SUSAR).

The DMC will be responsible for ongoing monitoring of the efficacy and safety of participants in the study according to the charter. The recommendations made by the DMC to alter the conduct of the study will be forwarded to the appropriate Pfizer personnel for final decision. Pfizer will forward such decisions, which may include summaries of aggregate analyses of endpoint events and of safety data that are not endpoints, to regulatory authorities, as appropriate.

10. SUPPORTING DOCUMENTATION AND OPERATIONAL CONSIDERATIONS

10.1. Appendix 1: Regulatory, Ethical, and Study Oversight Considerations

10.1.1. Regulatory and Ethical Considerations

This study will be conducted in accordance with the protocol and with the following:

- Consensus ethical principles derived from international guidelines including the Declaration of Helsinki and Council for International Organizations of Medical Sciences (CIOMS) International Ethical Guidelines
- Applicable ICH Good Clinical Practice (GCP) Guidelines
- Applicable laws and regulations, including applicable privacy laws.

The protocol, protocol amendments, ICF, Investigator Brochure, and other relevant documents (eg, advertisements) must be reviewed and approved by the sponsor and submitted to an IRB/IEC by the investigator and reviewed and approved by the IRB/IEC before the study is initiated.

Any amendments to the protocol will require IRB/IEC approval before implementation of changes made to the study design, except for changes necessary to eliminate an immediate hazard to study participants.

Protocols and any substantial amendments to the protocol will require health authority approval prior to initiation except for changes necessary to eliminate an immediate hazard to study participants.

The investigator will be responsible for the following:

- Providing written summaries of the status of the study to the IRB/IEC annually or more frequently in accordance with the requirements, policies, and procedures established by the IRB/IEC
- Notifying the IRB/IEC of SAEs or other significant safety findings as required by IRB/IEC procedures
- Providing oversight of the conduct of the study at the site and adherence to requirements of 21 CFR, ICH guidelines, the IRB/IEC, European regulation 536/2014 for clinical studies (if applicable), and all other applicable local regulations

10.1.1.1. Reporting of Safety Issues and Serious Breaches of the Protocol or ICH GCP

In the event of any prohibition or restriction imposed (ie, clinical hold) by an applicable regulatory authority in any area of the world, or if the investigator is aware of any new information that might influence the evaluation of the benefits and risks of the study intervention, Pfizer should be informed immediately.

In addition, the investigator will inform Pfizer immediately of any urgent safety measures taken by the investigator to protect the study participants against any immediate hazard, and of any serious breaches of this protocol or of ICH GCP that the investigator becomes aware of.

10.1.2. Financial Disclosure

Investigators and sub-investigators will provide the sponsor with sufficient, accurate financial information as requested to allow the sponsor to submit complete and accurate financial certification or disclosure statements to the appropriate regulatory authorities. Investigators are responsible for providing information on financial interests during the study and for 1 year after completion of the study.

10.1.3. Informed Consent Process

The investigator or his representative will explain the nature of the study to the participant and answer all questions regarding the study. The participant should be given sufficient time and opportunity to ask questions and to decide whether or not to participate in the trial.

Participants must be informed that their participation is voluntary. Participants will be required to sign a statement of informed consent that meets the requirements of 21 CFR 50, local regulations, ICH guidelines, privacy and data protection requirements, where applicable, and the IRB/EC or study center.

The investigator must ensure that each study participant is fully informed about the nature and objectives of the study, the sharing of data related to the study, and possible risks associated with participation, including the risks associated with the processing of the participant's personal data.

The participant must be informed that his personal study related data will be used by the sponsor in accordance with local data protection law. The level of disclosure must also be explained to the participant.

The participant must be informed that his medical records may be examined by Clinical Quality Assurance auditors or other authorized personnel appointed by the sponsor, by appropriate IRB/EC members, and by inspectors from regulatory authorities.

The investigator further must ensure that each study participant is fully informed about his right to access and correct his or her personal data and to withdraw consent for the processing of his or her personal data.

The medical record must include a statement that written informed consent was obtained before the participant was enrolled in the study and the date the written consent was obtained. The authorized person obtaining the informed consent must also sign the ICD.

Participants must be reconsented to the most current version of the IRB/EC-approved ICD(s) during their participation in the study as required per local regulation.

A copy of the ICD(s) must be provided to the participant.

Participants who are rescreened are required to sign a new ICD.

10.1.4. Data Protection

All parties will comply with all applicable laws, including laws regarding the implementation of organizational and technical measures to ensure protection of participant data.

Participants' personal data will be stored at the study site in encrypted electronic and/or paper form and will be password protected or secured in a locked room to ensure that only authorized study staff have access. The study site will implement appropriate technical and organizational measures to ensure that the personal data can be recovered in the event of disaster. In the event of a potential personal data breach, the study site will be responsible for determining whether a personal data breach has in fact occurred and, if so, providing breach notifications as required by law.

To protect the rights and freedoms of participants with regard to the processing of personal data, participants will be assigned a single, participant specific numerical code. Any participant records or data sets that are transferred to the sponsor will contain the numerical code; participant names will not be transferred. All other identifiable data transferred to the sponsor will be identified by this single, participant specific code. The study site will maintain a confidential list of participants who participated in the study, linking each participant's numerical code to his or her actual identity and medical record identification. In case of data transfer, the sponsor will protect the confidentiality of participants' personal data consistent with the clinical study agreement and applicable privacy laws.

Information technology systems used to collect, process, and store study-related data are secured by technical and organizational security measures designed to protect such data against accidental or unlawful loss, alteration, or unauthorized disclosure or access.

The sponsor maintains standard operating procedures on how to respond in the event of unauthorized access, use, or disclosure of sponsor information or systems.

10.1.5. Dissemination of Clinical Study Data

Data or results generated in the performance of the study may be used by sponsor for any purpose, including in registration documents for regulatory authorities in the US or abroad, or for public dissemination in the form of papers, abstracts, posters, or other informational materials to be presented at scientific meetings, or published in professional journals, or as a part of an academic thesis. Sponsor shall have the right to first publication of the data or results of the study, which is intended to be a joint, multi-center publication of the study results made by sponsor in conjunction with the investigators from all appropriate investigational sites contributing data, analysis and comments. Authorship of multi-center publications resulting from this study will be based on customary standards for attribution of authorship taking into consideration factors such as significance of contribution to the design of the study, analysis and interpretation of the data, and critical review of the publication. Subsequent to the first publication of the study results by sponsor, the investigator may publish the site-specific data or results. If the investigator wishes to publish the investigator's site specific data or results, a copy of such proposed publications, papers,

abstracts, or other written materials or an outline of any proposed oral presentations, shall be submitted to sponsor for review at least 60 days (or other number of days agreed to in the applicable clinical trial agreement governing the conduct of the study at the investigator's site) prior to submission of such written materials for publication, or any proposed oral presentation. Sponsor shall have the right to review and comment on such written material or outline, and to confirm the accuracy of the data described therein by comparison with that collected during the course of this study. In addition, sponsor may require investigator to, and investigator will, remove specifically identified confidential information of sponsor (other than the data or results of the study) and/or delay the proposed publication for an additional 60 days (or other number of days agreed to in the applicable clinical trial agreement governing the conduct of the study at the investigator's site) to enable sponsor to file patent applications.

Pfizer fulfills its commitment to publicly disclose clinical study results through posting the results of studies on www.clinicaltrials.gov (ClinicalTrials.gov), the EudraCT/CTIS, and/or www.pfizer.com, and other public registries in accordance with applicable local laws/regulations. In addition, Pfizer reports study results outside of the requirements of local laws/regulations pursuant to its SOPs.

In all cases, study results are reported by Pfizer in an objective, accurate, balanced, and complete manner and are reported regardless of the outcome of the study or the country in which the study was conducted.

www.clinicaltrials.gov

Pfizer posts clinical trial US Basic results on www.clinicaltrials.gov for Pfizer-sponsored interventional studies (conducted in participants) that evaluate the safety and/or efficacy of a product, regardless of the geographical location in which the study is conducted. These results are submitted for posting in accordance with the format and timelines set forth by US law.

EudraCT/CTIS

Pfizer posts clinical trial results on EudraCT/CTIS for all Pfizer-sponsored interventional studies in accordance with the format and timelines set forth by EU requirements.

www.pfizer.com

Pfizer posts CSR synopses and plain-language study results summaries on www.pfizer.com for Pfizer-sponsored interventional studies at the same time the corresponding study results are posted to www.clinicaltrials.gov. CSR synopses will have personally identifiable information anonymized.

Documents within marketing applications

Pfizer complies with applicable local laws/regulations to publish clinical documents included in marketing applications. Clinical documents include summary documents and CSRs

including the protocol and protocol amendments, sample CRFs, and SAPs. Clinical documents will have personally identifiable information anonymized.

Data Sharing

Pfizer provides researchers secure access to patient-level data or full CSRs for the purposes of “bona-fide scientific research” that contributes to the scientific understanding of the disease, target, or compound class. Pfizer will make available data from these trials 18 months after study completion. Patient-level data will be anonymized in accordance with applicable privacy laws and regulations. CSRs will have personally identifiable information redacted.

Data requests are considered from qualified researchers with the appropriate competencies to perform the proposed analyses. Research teams must include a biostatistician. Data will not be provided to applicants with significant conflicts of interest, including individuals requesting access for commercial/competitive or legal purposes.

